Gallium-68 PSMA-11 PET in patients with biochemical recurrence

Study Drug: Gallium-68 PSMA-11

Version Date: 08/27/2017

NCT# 03353740

Abstract

Title	Gallium-68 PSMA-11 PET in patients with biochemical recurrence
Patient population	
 • Rising PSA after definitive therapy with prostatectomy or radiation therapy (external beam or brachytherapy): 
 ○ Post radical prostatectomy (RP) – AUA recommendation 
 ▪ PSA greater than or equal to 0.2 ng/mL measured more than 6 weeks after RP. ○ Post-radiation therapy – ASTRO-Phoenix consensus definition 
 ▪ Nadir + greater than or equal to 2 ng/mL rise in PSA
Rationale for Study	Gallium-68 PSMA-11 has been shown to have a higher sensitivity for the detection of metastatic prostate cancer compared to choline based imaging.
Primary Objective	
 • Sensitivity on a per-patient and per-region-basis of ⁶⁸Ga-PSMA-11 PET for detection of tumor location confirmed by histopathology/biopsy, clinical and conventional imaging follow-up.
Secondary Objectives	
 • PPV on a per-patient and per-region-basis of ⁶⁸Ga-PSMA-11 PET for detection of tumor location confirmed by histopathology/biopsy, clinical and conventional imaging follow-up. • Sensitivity and positive predictive value (PPV) on a per-patient and per-region basis of ⁶⁸Ga-PSMA-11 PET for detection of tumor location confirmed by histopathology/biopsy. • Detection rates on a per-patient basis of ⁶⁸Ga-PSMA-11 PET stratified by PSA value (0.2 - <0.5, 0.5 - <1.0, 1.0 - <2.0, 2.0 - <5.0, ≥5.0). Detection rate will be stratified by history of prostatectomy, radiation or both; as well as by whether the patient is on androgen deprivation therapy (ADT). • Impact of ⁶⁸Ga-PSMA-11 PET on clinical management in BCR patients. • Inter-reader reproducibility. • Safety of ⁶⁸Ga-PSMA-11 administration as categorized by CTCAE 4.03.
Study Design	This is a phase 3 multi-center open label study.
Number of patients	Total population of patients will be 1,500 patients across all institutions.

Duration of Therapy	The study will involve a single imaging study.
Duration of Follow up	The patients will be followed-up by phone one day after the study completion, and clinical and imaging follow-up will last for up to 12 months after the PSMA-11 PET study..

1.1 Overview

Imaging and staging of prostate cancer is critical for surgical and treatment planning. We aim to image patients with suspected metastatic prostate cancer using Gallium-68 labeled HBED-CC PSMA (more commonly called ^{68}Ga -PSMA-11) in order to demonstrate its utility. We plan to utilize this data to obtain further approvals of the ^{68}Ga -PSMA-11 compound, so that this agent will become available for clinical imaging in prostate cancer patients.

This compound has been shown to be superior to choline based PET agents for the staging of prostate cancer, both Carbon-11 and Fluorine-18 compounds. But this compound was not patented and therefore no company or private entity will make the investment required to bring PSMA-11 to market. In the vacuum of availability, academic groups must take the lead in order to collect the necessary data for future FDA approval. This protocol was developed in collaboration with the Clinical Trials Network of the Society of Nuclear Medicine and Molecular Imaging. The inclusion criteria and study endpoints have been aligned so that inter-institutional sharing of data can be performed in order to pool data for final NDA submission.

1.2 Background

Prostate cancer is the most commonly diagnosed cancer and second leading cause of cancer death in American men (1). Existing conventional imaging (CT, MRI and bone scans) has a low sensitivity in detecting local recurrence or metastatic disease (2). The one exception being NaF PET/CT for the detection of osseous metastasis. Due to this limitation, numerous approaches to stage patients have been evaluated.

Choline imaging has been frequently used, as prostate cancer exhibits increase choline uptake that has been associated with the presence of choline kinase (3). Choline uptake is increased in comparison to FDG in both androgen dependent and independent prostate cancer patients (4). Choline has also been shown to be sensitive for the detection of recurrent tumor in patients with PSA (prostate specific antigen) values of less than 1.0 ng/ml (5). There are two forms of choline that are used in imaging prostate cancer, C-11 and F-18 choline. C-11 choline has a short half-life of 20 minutes, which limits its detection for metastatic disease but results in improved local detection due to decreased urinary activity at the time of imaging. F-18 choline has significant urinary excretion that limits evaluation of the prostate but, but has been shown to have better detection rates for distant metastatic disease (6). C-11 choline has limited sensitivity for osseous metastasis, possibly due to the decreased uptake time (7). Additionally, the sensitivity of C-11 choline is limited in patients with PSA values < 1.0 ng/ml (8-10). Although choline PET may be limited in sensitivity, it clearly delineates more lesions than cross section imaging or bone scan in patients with known disease (11). In 2012, the Mayo Clinic obtained NDA (new drug application) approval from the FDA for the use of C-11 choline.

A separate approach is to image the prostate specific membrane antigen (PSMA). PSMA is expressed on the majority of prostate cancer cells, and so would be an ideal cell membrane protein to image. The initial imaging approach to PSMA imaging target the intracellular domain using Indium-111-capromab (Prostascint), a murine monoclonal antibody (12,13). Although there was early promise for the detection of nodal metastasis (14), the agent was never able to adequately visualize osseous metastasis (15). Although combination with SPECT/CT does improve lesion detection (16). One main limitation to In-111-capromab is that it takes a prolonged time to localize to the target tissue, which likely relates to both the size of the monoclonal antibody and the fact that agent targets the intracellular domain of the PSMA protein. Additionally, Prostascint also recognizes an intracellular epitope so the antibody must

cross the membrane to be effective. This likely only occurs in permeable dead or dying tumor cells.

Because of the limitations of In-111 capromab, there has been continued effort to develop agents that target the extracellular domain of the PSMA protein. The Ga-68 labeled PSMA-11 compound has become of particular interest because in the last year there have been two important articles. The first demonstrates that PSMA-11 has a higher sensitivity for the detection of disease than F-18 choline in a head-to-head intra-patient comparison that included 37 patients (17). The second paper looked at the sensitivity of PSMA-11 in the detection of metastatic lesions in patients with recurrent prostate cancer (18). Their results demonstrated a detection rate of 50% for patients with a PSA less than 1 ng/ml, and detection rate above 85% for patients with a PSA greater than 2 ng/ml. These detection rates are significantly higher than that reported by groups using choline (5).

Because of the improved resolution and image quality with PET, ability to quantitate uptake, increased sensitivity compared to choline, we intend to evaluate the utility of Ga-68 PSMA-11 for the imaging of prostate cancer. We expect that the data from this study will support applications for clinical approval of this imaging agent, leading to wider availability within the United States.

1.3 Patient Population

Patients with biochemical recurrence after prostatectomy or radiation therapy:

- (a) Post radical prostatectomy (RP) – AUA recommendation
 - PSA greater than or equal to 0.2 ng/mL measured more than 6 weeks after RP.
- (b) Post-radiation therapy –ASTRO-Phoenix consensus definition
 - Nadir + greater than or equal to 2 ng/mL rise in PSA

2 Objectives of the Study

Region	Description
1	Prostate Bed
2	Pelvis outside of prostate bed including lymph nodes
3	Extrapelvic soft tissue, lymph nodes and organ metastases (non-bone)
4	Bone metastases

2.1 Primary

- Sensitivity on a per-patient and per-region-basis (Table 1) of ⁶⁸Ga-PSMA-11 PET for detection of tumor location confirmed by histopathology/biopsy, clinical and conventional imaging follow-up.

2.2 Secondary

- PPV on a per-patient and per-region-basis (Table 1) of ^{68}Ga -PSMA-11 PET for detection of tumor location confirmed by histopathology/biopsy, clinical and conventional imaging follow-up.
- Sensitivity and positive predictive value (PPV) on a per-patient and per-region-basis (Table 1) of ^{68}Ga -PSMA-11 PET for detection of tumor location confirmed by histopathology/biopsy.
- Detection rates on a per-patient basis of ^{68}Ga -PSMA-11 PET stratified by PSA value (0.2 - <0.5, 0.5 - <1.0, 1.0 - <2.0, 2.0 - <5.0, \geq 5.0). Detection rate will also be stratified by history of prostatectomy, radiation or both; as well as by whether the patient is on androgen deprivation therapy (ADT).
- Impact of ^{68}Ga -PSMA-11 PET on clinical management in BCR patients.
- Inter-reader reproducibility.
- Safety, as characterized by CTCAE 4.03.

3 Study Design

3.1 Characteristics

This is a prospective, Phase 3, multi-center, open-label study in patients with prostate cancer. Eligible participants will undergo baseline assessments at enrollment. Study participants will receive a one-time administration of Ga-68 PSMA-11 and undergo a PET/CT or PET/MRI imaging study.

3.2 Number of Subjects

It is anticipated that 1,500 patients will be enrolled in this study.

3.3 Eligibility Criteria

Patients must have baseline evaluations performed prior to the administration of the radiopharmaceutical and must meet all inclusion and exclusion criteria. In addition, the patient must be thoroughly informed about all aspects of the study, including the study visit schedule and required evaluations and all regulatory requirements for informed consent. The written informed consent must be obtained from the patient prior to enrollment. The following criteria apply to all patients enrolled onto the study:

3.3.1 Inclusion Criteria

1. Histopathologically proven prostate adenocarcinoma.
2. Rising PSA (at least two consecutive rising PSAs) after definitive therapy with prostatectomy or radiation therapy (external beam or brachytherapy).
 - a. Post radical prostatectomy (RP) – AUA recommendation for biochemical recurrence after radical prostatectomy
 - i. PSA greater than or equal to 0.2 ng/mL measured more than 6 weeks after RP.

- b. Post-radiation therapy –ASTRO-Phoenix consensus definition of biochemical recurrence after radiation therapy
 - i. Nadir + greater than or equal to 2 ng/mL rise in PSA
3. Karnofsky performance status of ≥ 50 (or ECOG/WHO equivalent).
4. Age > 18.
5. Ability to understand a written informed consent document, and the willingness to sign it.

3.3.2 Exclusion Criteria

1. Unable to lie flat, still or tolerate a PET scan.
2. Concomitant investigational therapy.
3. Patient undergoing active treatment for non-prostate malignancy, other than skin basal cell or cutaneous superficial squamous cell carcinoma that has not metastasized and superficial bladder cancer.
4. Contraindication to furosemide administration including prior allergy or adverse reaction to furosemide or sulfa drugs. (Note: This exclusion criteria can be removed if Furosemide is omitted as part of the PET imaging protocol if a second-generation scatter correction is available for the used PET device).

3.4 Duration of Follow Up

Patients will be followed for one day after the administration of the radiopharmaceutical.

3.5 Study Timeline

3.5.1 Primary Completion

The study will reach primary completion 36 months from the time the study opens to accrual.

3.5.2 Study Completion

The study will reach study completion 48 months from the time the study opens to accrual.

4 Study Drugs

4.1 Description, Supply and Storage of Investigational Drugs

4.1.1 Investigational Drug #1

Ga-68 labeled PSMA-11 (or PSMA-HBED-CC) is a radiopharmaceutical that will be produced under cGMP.

5 Treatment Plan

5.1 Dosage and Administration

The imaging agent (Ga-68 PSMA-11 or PSMA-HBED-CC) will be administered on an outpatient basis. It will be administered a single time intravenously prior to the PET imaging. The injected dose will be 3 to 7 mCi of ^{68}Ga -PSMA-11.

5.1.1 Other Modality(ies) or Procedures

5.1.1.1 Change in management surveys

Referring clinicians will be required to fill out a pre-imaging survey prior to imaging. Please see Appendix 3. Additionally within 30 days of the completion of imaging, the referring physician will be requested to fill out a post-imaging survey, and finally three to six months after imaging, a third survey will be filled out.

5.1.1.2 PET imaging

a) ^{68}Ga -PSMA-11 PET preparation and injection:

The intravenously injected dose will be 111-259 MBq (3-7 mCi) of ^{68}Ga -PSMA-11 PET. A dose of 20 mg of furosemide (Lasix) is recommended to be injected i.v. together with, shortly before or after administration of the radiotracer in order to minimize PET scatter artifacts from excreted radiotracer accumulation in the kidney and urinary bladder that can occur with the gallium-68 radionuclide. Oral hydration is recommended on the day of the scan. Voiding is recommended immediately before start of the scan. Furosemide should not be administered in patients with medical contraindications to Furosemide administration including allergies and adverse reactions including sulfa allergies. (Note: Application of Furosemide can be omitted as part of the PET imaging protocol if a second-generation scatter correction algorithm is available for the PET scanner used in this protocol). PET imaging will begin 50-100 minutes after injection. Scan time per bed position will be determined based on each sites PET scanner capabilities.

b) Patient preparation: no fasting is required.

c) PET protocol: Scan coverage will extend from mid thigh to the base of the skull, starting from the mid-thighs to prevent urinary bladder radiotracer accumulation at the start of PET imaging. Bed position scan time will be dependent on each sites scanner capabilities. At a minimum, 3 minutes per bed position will be used. In certain circumstances, coverage may be extended to the toes. Contrast may be administered if requested by the referring clinician and is decided site dependent.

d) Patient monitoring: Vital signs will be assessed immediately before and after injection of ^{68}Ga -PSMA-11 (HR and supine BP). Patients will be monitored for adverse events during injection and for two hours after radiotracer administration. Additionally, patient's vitals (HR and supine BP) will be checked at the completion of the imaging study prior to leaving the imaging center.

e) Patient follow-up: Patients will be contacted one to three days after ^{68}Ga -PSMA-11 PET to assess for the development of delayed adverse events. Patients will be seen in the clinic if there are any concerning study related adverse events requiring further evaluation. Patients will also be followed up clinically and using conventional imaging for up to 12 months after ^{68}Ga -PSMA-11 PET. Follow-up imaging will be performed as allowed under standard of care.

5.2 Monitoring and Toxicity Management

Each patient receiving Ga-68 PSMA-11 will be evaluable for safety. The safety parameters include physical findings and spontaneous reports of adverse events reported to the investigator by patients.

6 Study Procedures and Observations (Appendix 2)

6.1 Schedule of Procedures and Observations

Screening assessments must be performed within 30 days prior to the first dose of investigational product. Any results falling outside of the reference ranges may be repeated at the discretion of the investigator. Treatment or visit delays for public holidays or weather conditions do not constitute a protocol violation.

A written, signed, informed consent form (ICF) and a Health Insurance Portability and Accountability Act (HIPAA) authorization must be obtained before any study-specific assessments are initiated. A copy of the signed ICF will be given to the subject and a copy will be filed in the medical record. The original will be kept on file with the study records.

6.1.1.1 Screening Assessments

The Screening procedures and assessments must be completed within 30 days of the day 1 Visit.

- Laboratory values: all patients must have a recent PSA (within 30 days prior to study enrollment) consistent with BCR
 - If only one PSA greater than or equal to 0.2 ng/dL post radical prostatectomy is available, then a second confirmatory PSA must be checked prior to the ⁶⁸Ga-PSMA-11 PET study.
- Pathology: all patients must have histopathology/biopsy of the prostate with a documented Gleason score
- Performance status: all patients must have their Karnofsky performance status (or ECOG/WHO equivalent) evaluated (Appendix 1).
- Change in management: A pre-imaging survey of planned clinical management will be performed prior to ⁶⁸Ga PSMA-11 PET/CT imaging.

6.1.2 Treatment Period

6.1.2.1 Study Procedures, Imaging Day 1

- Vital signs
- Evaluation of adverse events

6.1.3 Post-treatment Follow Up Visits

Patients will be followed for 1-3 days after enrollment, by phone. The following procedure will be performed:

- Evaluation of adverse events

Additionally, the following post-treatment follow up will be performed:

- Change in management: A post-imaging survey of clinical management using PSMA-11 PET/CT information will be performed ≤ 30 days of PSMA-11 PET/CT imaging for assessment of change in clinical management.

- Change in management 6 months post imaging: A survey of clinical management will be performed approximately 6 months after the PSMA-11 PET/CT imaging for assessment of change in clinical management.
- Conventional imaging follow-up 3-12 months post imaging: Conventional imaging follow-up shall be performed as per institutional standard of care. DICOM images /or associated report should be collected for analysis.

6.2 Prohibited Medications

There are no prohibited medications.

7 Reporting and Documentation of Results

7.1 Evaluation of Side Effects

7.1.1.1 Definitions

Evaluable for toxicity

All patients will be evaluable for toxicity from the time of ⁶⁸Ga-PSMA-11.

7.2 Evaluation of Safety

Analyses will be performed for all patients receiving ⁶⁸Ga-PSMA-11. The study will use the [CTCAE v4.0](#) for reporting of adverse events.

7.3 Definitions of Adverse Events

7.3.1 Adverse Event

An adverse event (also known as an adverse experience) is defined as any untoward medical occurrence associated with the use of a drug in humans, whether or not considered drug related. More specifically, an adverse event (can be any unfavorable and unintended sign (e.g., an abnormal laboratory finding), symptom, or disease temporally associated with the use of a drug, without any judgment about causality. An adverse event can arise from any use of the drug (e.g., off-label use, use in combination with another drug) and from any route of administration, formulation, or dose, including an overdose.

7.3.2 Adverse reaction

An adverse reaction is defined as any adverse event caused by the use of a drug. Adverse reactions are a subset of all suspected adverse reactions for which there is reason to conclude that the drug caused the event.

7.3.2.1 Suspected

A suspected adverse reaction is defined as any adverse event for which there is a reasonable possibility that the drug caused the adverse event. For the purposes of IND safety reporting, "reasonable possibility" indicates that there is evidence to suggest a causal relationship between the drug and the adverse event. A suspected adverse reaction implies a lesser degree of certainty about causality than an adverse reaction.

7.3.2.2 Unexpected

An adverse event or suspected adverse reaction is considered *unexpected* if it is not listed in the investigator brochure or package insert(s), or is not listed at the specificity or severity that has been observed, or, if an investigator brochure is not required or available, is not consistent with the risk information described in the general investigational plan or elsewhere in the current application.

“Unexpected,” as used in this definition, also refers to adverse events or suspected adverse reactions that are mentioned in the investigator brochure as occurring with a class of drugs or as anticipated from the pharmacological properties of the drug, but are not specifically mentioned as occurring with the particular drug under investigation.

Adverse events that would be anticipated to occur as part of the disease process are considered *unexpected* for the purposes of reporting because they would not be listed in the investigator brochure. For example, a certain number of non-acute deaths in a cancer trial would be anticipated as an outcome of the underlying disease, but such deaths would generally not be listed as a suspected adverse reaction in the investigator brochure.

7.3.2.3 Serious

An adverse event or suspected adverse reaction is considered *serious* if, in the view of either the investigator or sponsor, it results in any of the following outcomes:

- Death
- Life-threatening adverse event
- Inpatient hospitalization or prolongation of existing hospitalization
- A persistent or significant incapacity or substantial disruption of the ability to conduct normal life function
- Congenital anomaly/birth defect

Important medical events that may not result in death, are life-threatening, or require hospitalization may be considered serious when, based upon appropriate medical judgment, they may jeopardize the patient or subject and may require medical or surgical intervention to prevent one of the outcomes listed in this definition. Examples of such medical events include allergic bronchospasm requiring intensive treatment in an emergency room or at home, blood dyscrasias or convulsions that do not result in inpatient hospitalization, or the development of drug dependency or drug abuse.

7.3.2.4 Life-threatening

An adverse event or suspected adverse reaction is considered *life-threatening* if, in the view of either the investigator or sponsor, its occurrence places the patient or subject at immediate risk of death. It does not include an adverse event or suspected adverse reaction that, had it occurred in a more severe form, might have caused death.

7.4 Recording of an Adverse Event

All grade 3 and above adverse events will be recorded using the NCI CTCAE v4.0. The Investigator will assign attribution of the possible association of the event with use of the investigational drug.

Relationship	Attribution	Description
Unrelated to investigational drug/intervention	Unrelated	The AE is clearly NOT related to the intervention
	Unlikely	The AE is doubtfully related to the intervention
Related to investigational drug/intervention	Possible	The AE may be related to the intervention
	Probable	The AE is likely related to the intervention
	Definite	The AE is clearly related to the intervention

Signs or symptoms reported as adverse events will be graded and recorded by the Investigator according to the CTCAE. When specific adverse events are not listed in the CTCAE they will be graded by the Investigator as *none, mild, moderate* or *severe* according to the following grades and definitions:

- Grade 0 No AE (or within normal limits)
- Grade 1 Mild; asymptomatic or mild symptoms; clinical or diagnostic observations only; intervention not indicated
- Grade 2 Moderate; minimal, local, or noninvasive intervention (e.g., packing, cautery) indicated; limiting age-appropriate instrumental activities of daily living (ADL)
- Grade 3: Severe or medically significant but not immediately life-threatening; hospitalization or prolongation of hospitalization indicated; disabling; limiting self-care ADL
- Grade 4: Life-threatening consequences; urgent intervention indicated
- Grade 5: Death related to AE

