8.3.3 Analysis of Secondary Endpoints

1. PPVs on a per-patient and per-region-basis of ^{68}Ga -PSMA-11 PET for detection of tumor location confirmed by histopathology/biopsy, clinical and conventional imaging follow-up will be calculated and reported along with the corresponding two-sided 95% confidence intervals. The confidence intervals will be constructed using the Wilson score method. PPV will be reported for each of the three blinded readers independently.
2. Sensitivity and PPVs on a per-patient and per-region basis of ^{68}Ga -PSMA-11 PET for detection of tumor location confirmed by histopathology/biopsy will be summarized in tabular format. Ninety-five percent confidence intervals of sensitivity, specificity, NPV and PPV will be calculated using the Wilson score method. These will be reported for each of the three blinded readers.
3. Detection rates on a per-patient basis of ^{68}Ga -PSMA-11 PET stratified by PSA value (0.2 - <0.5, 0.5 - <1.0, 1.0 - <2.0, 2.0 - <5.0, ≥ 5.0) will be summarized in tabular format and compared between PSA strata using chi-square analysis. Detection rate will also be stratified by history of prostatectomy, radiation or both; as well as by whether the patient is on androgen deprivation therapy (ADT). We will use local interpretations for this analysis.
 - a. Detection rate is defined as number of patients with PSMA positive disease, independent of pathology, imaging or clinical follow-up. A detection rate will be reported for each reader independently stratified by PSA.
4. The impact of ^{68}Ga -PSMA-11 PET on clinical management in BCR patients will be evaluated using descriptive statistics.
5. Inter-reader reproducibility for positivity at the patient level and region level will be reported using the Fleiss' Kappa test for multiple readers. We will use the three blinded reads for this analysis.
6. Safety will be reported descriptively as rates of patient reported adverse events. Additionally, adverse events will be characterized and quantified by CTCAE 4.03.

9 Study Management

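### Section 7.4 gives both a grade 3+ recording rule and one with no grade floor, while the safety endpoint has no grade limit, so grade 1–2 events could be omitted or recorded unevenly across sites

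*Combined protocol and SAP*

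**What the plan says.** Section 7.4, which governs recording, contains two statements about which events go on record. It opens with "All grade 3 and above adverse events will be recorded using the NCI CTCAE v4.0". The instruction to assign attribution, and the attribution table, follow directly. After the table comes the second statement: "Signs or symptoms reported as adverse events will be graded and recorded by the Investigator according to the CTCAE". A scale from grade 0 to grade 5 is then given for events that CTCAE does not list. It includes an entry for the mildest events: "Grade 1 Mild; asymptomatic or mild symptoms; clinical or diagnostic observations only; intervention not indicated".

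The analysis is in 8.3.3, item 6, and has two parts: "Safety will be reported descriptively as rates of patient reported adverse events", and then "Additionally, adverse events will be characterized and quantified by CTCAE 4.03". The matching objective in 2.2 reads "Safety, as characterized by CTCAE 4.03". None of these sets a minimum grade.

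**The concern.** The opening sentence of the recording section names a grade threshold. If every grade is to be recorded anyway, the threshold does no work, so a study coordinator could reasonably take it to mean that recording starts at grade 3. The later sentence can then be read as describing how to grade an event, a step needed before the threshold can be applied.

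On that reading the recorded data would be narrower than the endpoint they feed. Three features of the trial make this matter:

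- Safety is a stated secondary objective.
- The study is multi-center (3.1), and 1.1 says that data are to be pooled between institutions for a marketing application. Different readings of 7.4 would mix grade cut-offs within one rate.
- The analysis could not repair the loss. Patients are monitored for two hours after administration and contacted once, one to three days later (5.1.1.2, items d and e). A mild event left unrecorded at those points may not be recoverable.

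**Working it through.** The plan states no adverse event rate or grade distribution, so there is no figure to reproduce. The check is a comparison of every statement on recording, collecting and analyzing adverse events, followed by simple algebra.

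**Step 1. Grade limits, section by section.**

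- 7.4, opening sentence: grade 3 and above. The word *only* does not appear.
- 7.4, later sentence: no grade floor, and the scale that follows defines grades 1 and 2.
- 2.2 and 8.3.3, item 6: no grade limit.
- 5.2: no grade limit; "The safety parameters include physical findings and spontaneous reports of adverse events reported to the investigator by patients".
- 7.2: "Analyses will be performed for all patients receiving" the agent, no grade limit.
- 7.5: follow-up applies to adverse events without a grade limit.
- Appendix 2: lists adverse event reporting without a grade.

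One sentence carries a threshold and the others do not. Appendix 2 does not settle which of the two sentences in 7.4 a site should follow.

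**Step 2. Can both sentences of 7.4 be obeyed?** Yes. A site that records every reported event breaches neither. A site that records from grade 3 up satisfies the first but not the plain wording of the second. The text therefore leans towards all grades but leaves the narrower practice open.

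**Step 3. Attribution.** The attribution instruction is attached to the grade 3+ sentence. Even where low-grade events are recorded, 7.4 does not make clear whether they need an attribution.

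**Step 4. Size.** Let s be the share of all events that are grade 1–2.

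- If the later sentence governs everywhere, the share omitted is 0.
- If the opening sentence alone governs everywhere, the share recorded is 1 − s and the share omitted is s.
- If a fraction p of events arises at sites that apply the threshold, and the grade mix is the same at all sites, the share omitted is p × s, which lies between 0 and s.

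The documents do not give s. Assumed values show the range under the threshold reading: s = 0.5 gives 1 − 0.5 = 50% recorded and 50% omitted; s = 0.9 gives 10% recorded and 90% omitted; s = 1.0 gives none recorded. If the rate counts patients rather than events, the same algebra applies with s as the share of affected patients whose worst event is grade 1 or 2.

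**Step 5. CTCAE version.** Sections 7.2 and 7.4 cite v4.0, while 2.2 and 8.3.3 cite 4.03. This is a separate, smaller mismatch that the same edit can close.

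**The case against.** The strongest reply is that 7.4, read as a whole, already requires low-grade events to be recorded. The opening sentence sets a minimum and does not exclude anything. It may serve mainly to introduce attribution. The later sentence uses the word recorded and has no floor, and a scale that defines grades 1 and 2 would be odd if those grades were never kept. Collection is described without a grade limit elsewhere too. The two parts of 8.3.3, item 6, are also separate: a sentence about recording under CTCAE need not restrict the patient-reported rate. The case report form is not among the documents, so it may already capture every grade.

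Much of this stands. A reader might infer that the plan captures events only from grade 3 upward and will certainly under-report. The documents do not support that: the opening sentence does not say *only*, and the later one points the other way. Nor does 8.3.3 say *all* patient-reported events; it simply sets no limit. A reader might also be tempted to state a fold under-count, or an upper confidence bound for a zero count. The first would rest wholly on assumed event rates and grade mix. The second is not a planned output, since safety is to be reported descriptively. Grade 3+ events would remain poolable under either practice.

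What does not stand is the conclusion that nothing needs changing. The favorable reading leaves the threshold without a function, and neither 8.3.3 nor Appendix 2 tells a site which sentence to apply.

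**Conclusion.** The point holds as an internal inconsistency in what is recorded. Section 7.4 states a grade 3+ rule and a rule with no floor, and the safety endpoint has no grade limit. Omission of grade 1–2 events, and different cut-offs between sites, are possible but not established. The share of events omitted runs from zero, if the later sentence is followed everywhere, to the full grade 1–2 share, if the opening sentence is. The documents do not allow that range to be narrowed. The conclusion rests on the wording alone and assumes nothing about the safety profile of the agent. It should be corrected, because a lost low-grade event cannot be restored at analysis and the correction is nearly free.

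**What to change.** Replace the opening sentence of 7.4 with a rule to this effect: adverse events of any grade, reported by the patient or observed by staff, from administration of the agent onward and including the 1–3 day contact, will be recorded, graded by CTCAE 4.03 and given an attribution; grade 3 and above will also be reported as a subset. Cite the same CTCAE version in 7.2. In 8.3.3, item 6, state that the rates cover all grades, so that the grades recorded match the grades analyzed.

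The cost is a protocol amendment and a few extra lines on the case report form. No new visit or contact is needed, because adverse events are already to be evaluated on the imaging day and at the follow-up contact (6.1.2.1 and 6.1.3).
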